**Table 16-2 Follow-Up Requirements for Liver Events and Laboratory Triggers**

Criteria	Actions required	Follow-up monitoring
Potential Hy's Law case a	
 
Discontinue the study treatment immediately
 
Hospitalize, if clinically appropriate
 
Establish causality
 
Complete liver CRF
 
	ALT, AST, TBL, Alb, PT/INR, ALP and γGT until resolution c (frequency at investigator discretion)
ALT or AST		
> 8 × ULN	
 
Discontinue the study treatment immediately
 
Hospitalize if clinically appropriate
 
Establish causality
 
Complete liver CRF
 
	ALT, AST, TBL, Alb, PT/INR, ALP and γGT until resolution c (frequency at investigator discretion)
> 3 × ULN and INR > 1.5	
 
Discontinue the study treatment immediately
 
Hospitalize, if clinically appropriate
 
Establish causality
 
Complete liver CRF
 
	ALT, AST, TBL, Alb, PT/INR, ALP and γGT until resolution c (frequency at investigator discretion)

Criteria	Actions required	Follow-up monitoring
> 5 to ≤ 8 × ULN	
 
Repeat LFT within 48 hours
 
If elevation persists, continue follow-up monitoring
 
If elevation persists for more than 2 weeks, discontinue the study drug
 
Establish causality
 
Complete liver CRF
 
	ALT, AST, TBL, Alb, PT/INR, ALP and γGT until resolution c (frequency at investigator discretion)
> 3 × ULN accompanied by symptoms b	
 
Discontinue the study treatment immediately
 
Hospitalize if clinically appropriate
 
Establish causality
 
Complete liver CRF
 
	ALT, AST, TBL, Alb, PT/INR, ALP and γGT until resolution c (frequency at investigator discretion)
> 3 to ≤ 5 × ULN (subject is asymptomatic)	
 
Repeat LFT within the next week
 
If elevation is confirmed, initiate close observation of the subject
 
	Investigator discretion Monitor LFT within 1 to 4 weeks
ALP (isolated)		
> 2 × ULN (in the absence of known bone pathology)	
 
Repeat LFT within 48 hours
 
If elevation persists, establish causality
 
Complete liver CRF
 
	Investigator discretion Monitor LFT within 1 to 4 weeks or at next visit
TBL (isolated)		
> 2 × ULN (in the absence of known Gilbert syndrome)	
 
Repeat LFT within 48 hours
 
If elevation persists, discontinue the study drug immediately
 
Hospitalize if clinically appropriate
 
Establish causality
 
Complete liver CRF
 
	ALT, AST, TBL, Alb, PT/INR, ALP and γGT until resolution c (frequency at investigator discretion) Test for hemolysis (e.g. reticulocytes, haptoglobin, unconjugated [indirect] bilirubin)
> 1.5 to ≤ 2 × ULN (subject is asymptomatic)	
 
Repeat LFT within the next week
 
If elevation is confirmed, initiate close observation of the subject
 
	Investigator discretion Monitor LFT within 1 to 4 weeks or at next visit
Jaundice	
 
Discontinue the study treatment immediately
 
Hospitalize the subject
 
Establish causality
 
Complete liver CRF
 
	ALT, AST, TBL, Alb, PT/INR, ALP and γGT until resolution c (frequency at investigator discretion)
Any AE potentially indicative of a liver toxicity*	
 
Consider study treatment interruption or discontinuation
 
Hospitalization if clinically appropriate
 
Establish causality
 
Complete liver CRF
 
	Investigator discretion
a Elevated ALT/AST > 3 × ULN and TBL > 2 × ULN but without notable increase in ALP to > 2 × ULN b (General) malaise, fatigue, abdominal pain, nausea, or vomiting, or rash with eosinophilia c Resolution is defined as an outcome of one of the following: (1) return to baseline values, (2) stable values at three subsequent monitoring visits at least 2 weeks apart, (3) remain at elevated level after a maximum of 6 months, (4) liver transplantation, and (5) death.		

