### 3 Study design

This is a multicenter, open-label, study to assess the pharmacokinetics, safety, and tolerability of fevipiprant CT in children aged 6 to < 12 years with asthma. The study includes a 4-8 day, open-label treatment period in which subjects receive fevipiprant CT once daily (o.d.) in addition to their rescue medication (e.g. short-acting  $\beta$ -agonists [SABAs]) and potentially standard-of-care (SoC) asthma therapy (inhaled corticosteroids [ICS] with or without an additional controller therapy). There will be 2 treatment dose cohorts studied (fevipiprant 75 mg o.d. and one higher dose selected based on PK obtained at 75 mg/day, [e.g. 150, 225, 300, or 375 mg once daily]). Within each dose cohort, subjects will be stratified approximately 1:1 ratio into 2 age groups: ages 6 to < 9 years and ages 9 to < 12 years.

The study will include the following:

- A Screening period of up to 14 days;
- A Treatment period of 4-8 days for each dose cohort (8 days of treatment is preferred); and
- A Follow-up period of 30 days

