#### **End of Treatment Visit (Day 4 to 8)**

The End of Treatment Visit can only occur after 3 consecutive days of dosing (i.e., as early as Day 4 of dosing).

At the EOT Visit Day, subjects should not take the study drug at home, and arrive at the site or planned remote visit in the morning. Study drug will be taken in the clinic/home, and PK

sampling will occur over 8 hours; the subject and parent/guardian will need to be available to remain in the clinic/home for about 8 to 9 hours.

The scheduling and timing of EOT Visit should ensure dosing of study drug in the clinic/home takes place about  $24 \pm 2$  hours after the last dose of study drug taken at home. On the day prior to EOT, visit study personnel should remind the subject and parent/guardian in a phone call to take study medication at the right time in relation to the scheduled EOT visit. Additionally, PK sampling requires confirmation that study drug was taken for 3 consecutive days prior to EOT Visit. This information must be confirmed by study personnel/remote nurse at EOT Visit by the review of the subject's daily dosing diary. If study personnel/remote nurse cannot confirm that study drug was taken by the subject on 3 consecutive days prior to EOT Visit, the EOT Visit can be rescheduled for +1 to 2 days later. In cases where the subject cannot make the scheduled EOT Visit or has mistakenly taken the study drug at home on the Day of EOT Visit, the Visit can be re-scheduled to the next available clinic/home day.

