At the start of the EOT Visit, eligibility to proceed with PK assessments will be confirmed and subjects will receive a light breakfast (e.g. average sized serving of cereal, milk, banana, and/or yogurt) at the study site about 30 minutes prior to dosing. Prior to dosing subjects should be encouraged to empty their bladder in the rest room (not collected for urine PK sampling, but can be used for urine dipstick) in order to get a clear pool of urine post dosing, used for urine PK sampling. Subjects will be administered the final dose of study drug by study staff within approximately 30 minutes after completion of breakfast. Subjects will be instructed to chew small piece of banana/yogurt followed immediately by CT(s) and then followed with an additional piece of banana/yogurt. Subjects will be encouraged to drink some water thereafter. The procedures associated with EOT Visit (including the placement of an indwelling catheter with local anesthetic for blood draws) will be performed in the clinic/home as outlined in [Table 8-1](#). [Section 16.4](#) outlines the PK and vital sign (VS) timing of assessments noting that at time points where multiple procedures occur; the following order is recommended: VS, e.g. PK sampling, laboratory blood draws.

The time of dosing for witnessed dose of fevipiprant CT will be recorded in the eCRF. Throughout the visit, subjects should be encouraged to drink water in order to allow urine production for urine collection.

Blood for PK sampling may be drawn via intermittent venous punctures with topical anesthetic or via the placement of an indwelling catheter with local anesthetic. PK sampling will be obtained as close as feasible to planned times with the actual times of blood draws recorded in source and on the eCRF.

In addition to breakfast, subjects may have food during their time at the clinic/home, but it is recommended that they wait at least 3 hours after dosing to eat.

To avoid the need for an overnight stay at the clinical site, the pre-dose drug concentration values obtained on EOT Visit will also be used as the 24-hour post-dose drug concentration value to calculate AUC0-24,ss. For this reason it is important to have approximately 24 h between the last at home dose and the witnessed dose in the clinic at the EOT Visit.

Upon completion of all EOT Visit study assessments, at the investigator's discretion, the subject may go home.

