#### **4.5 Risks and benefits**

Fevipirant is a potent and highly selective oral DP2 (also referred to as CRTh2) receptor antagonist being developed as a potential therapy treatment for subjects with severe asthma. DP2 is a receptor for PGD2 which mediates the activation and migration of Th2 cells and eosinophils, some of the key inflammatory cell types in asthma. Recruitment of these cells into the lung is partly responsible for the intermittent airway obstruction which leads to wheezing and shortness of breath characteristic of asthma.

Fevipirant is at least 300-fold selective for the DP2 receptor compared to other available prostanoid receptors and to cyclooxygenase-1 and cyclooxygenase-2, and it has been demonstrated to be a potent *in vitro* inhibitor of human whole blood eosinophil activation and induction of Th2 cytokines. After oral dosing in rats, QAW039 inhibited pulmonary eosinophilia induced by the PGD2 metabolite DK-PGD2.

The potential benefits of QAW039 therapy need to be balanced against its potential risks. The risk to subjects in this study will be minimized by compliance with the inclusion/exclusion criteria and close clinical monitoring. All subjects will remain on the background SoC asthma therapy they were taking at screening throughout the study, with exemption of LTRAs (LTRAs have to be stopped but in that case ICS can be initiated or dosed higher in case the subject was already on ICS). Furthermore, subjects will be instructed how to react to worsening of asthma symptoms so subjects can be managed appropriately.

Appropriate eligibility criteria and specific dose-limiting toxicity definitions, as well as specific dose modification and stopping rules, are included in this protocol.

All assessments in this trial are relatively small and part of regular medical assessments in this subject population. Procedural risks are related to blood sampling for safety and PK laboratory analyses: puncturing of the veins can cause discomfort, pain, hematoma or in rare cases lead to an infection.

The overall clinical experience with fevipirant includes 24 studies: 15 (nine in healthy volunteers and six in patients) have completed and nine (five in asthma subjects, 2 in healthy volunteers and 2 in subjects with renal or hepatic impairment) are ongoing. The completed Phase II studies consist of four in subjects with asthma, one in subjects with allergic rhinitis and

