## 5.2 Exclusion criteria

Subjects meeting any of the following criteria are not eligible for inclusion in this study.

1. Use of other investigational drugs within 5 half-lives of enrollment, or (within 30 days (for small molecules)/until the expected pharmacodynamic effect has returned to baseline (for biologics)), whichever is longer.
2. Subject is unable to ingest banana and/or yogurt
3. History of hypersensitivity to any of the study drugs or its excipients or to drugs of similar chemical classes.
4. History of chronic lung disease other than asthma such as and not limited to, sarcoidosis interstitial lung disease, cystic fibrosis, mycobacterial or other infection (including active tuberculosis or atypical mycobacterial disease).
5. History of active bacterial, viral or fungal infection within 6 weeks of Treatment Visit (Day 1).
6. Subjects who, in the opinion of the investigator, are not able to be compliant with study treatment or who have any medical or mental disorder, situation, or diagnosis, which could interfere with the proper completion of the protocol requirements or risk the subject's safety while participating in the study.
7. Parent/guardian who, in the opinion of the investigator, has a history of psychiatric disease, intellectual deficiency, substance abuse, or other condition (e.g. inability to read, comprehend and write) which will limit the validity of consent for their child to participate in this study.
8. Hemoglobin levels outside normal ranges at screening.
9. Any surgical or medical condition which might significantly alter the absorption, distribution, metabolism, or excretion of drugs, or which may jeopardize the subject in case of participation in the study.

10. Subjects who have a clinically significant ECG abnormality or clinically significant abnormal lab values reported at Screening Visit.
11. Subjects with a history of long QT syndrome or whose corrected QT interval (QTc) measured at Screening Visit (Fridericia method) is prolonged ( $\geq 450$  msec for boys and girls).
12. Subjects receiving any medications in the classes specified in [Table 6-3](#) unless they undergo the required washout period prior to Treatment Visit (Day 1) and follow the adjustment through the treatment period.
13. Subjects receiving medications in the classes listed in [Table 6-2](#) should be excluded unless the medication has been stabilized for the specified period and the stated conditions have been met.

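### The mandatory stop for ALT or AST >5 to ≤8 × ULN needs more than two weeks of persistence, so it cannot act within a 4–8 day course; the gap is small

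*Protocol*

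**What the plan says.** Protocol Section 16.2, Table 16-1, classes ALT or AST above 5 × ULN as a liver event. For the band above 5 and up to 8 × ULN, Table 16-2 asks for a repeat within 48 hours, continued monitoring if the elevation persists, and then: "If elevation persists for more than 2 weeks, discontinue the study drug". The row also asks for a causality assessment, a liver CRF and liver tests until resolution.

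Section 3 sets the length of dosing: "A Treatment period of 4-8 days for each dose cohort (8 days of treatment is preferred". The last dose is given at the EOT visit: "Subjects will be administered the final dose of study drug by study staff within approximately 30 minutes after completion of breakfast". If dosing on the three preceding days cannot be confirmed, "the EOT Visit can be rescheduled for +1 to 2 days later". A missed visit, or a dose taken at home that morning, moves the visit to the next day that can be arranged, with no limit stated. The 30-day follow-up is drug-free.

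In the same table, the row for isolated total bilirubin above 2 × ULN has a repeat within 48 hours and then: "If elevation persists, discontinue the study drug immediately". Immediate stops also apply to ALT or AST above 8 × ULN, to ALT or AST above 3 × ULN with INR above 1.5 or with listed symptoms, to potential Hy's Law cases and to jaundice.

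**The concern.** A stop that needs more than 14 days of observation has been placed in a trial that doses for at most about 10 days. It is the only mandatory stop written for this liver event when none of the immediate-stop features is present. While the child is still being dosed, the row's instruction for a confirmed elevation is to keep monitoring.

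Section 4.5 tells readers that eligibility criteria and toxicity definitions, "as well as specific dose modification and stopping rules, are included in this protocol". For this one band, a reader who relies on the table would think a mandatory stop is in place when it cannot take effect before dosing is over. At stake is a small number of further doses in a child with a confirmed transaminase elevation, in the first study of the drug in this age range.

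**Working it through.** This is calendar arithmetic; no sample-size or error-rate formula is involved.

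**Inputs**
- Persistence required: more than 14 days (Table 16-2).
- Last dose day *L*: Day 4 to Day 8 (Section 3); with the +1 to 2 day reschedule, 8 + 2 = Day 10.
- Repeat test: within 48 hours (Table 16-2).
- Scheduled safety blood: Screening and EOT pre-dose only (Tables 16-3 and 16-5).

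**Check on the dosing window.** Table 8-1 puts the 30-day follow-up contact at Days 34 to 38. 4 + 30 = 34 and 8 + 30 = 38, so a last dose on Day 4 to 8 is confirmed.

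**Earliest day the stop can act.** For a first elevated sample on Day *d*, two weeks have passed on Day *d* + 14, and the first whole day beyond two weeks is Day *d* + 15. The start most favourable to the rule is *d* = 1, giving Day 15 or Day 16.

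| Last dose | Days from last dose to Day 15 | Days from last dose to Day 16 |
|---|---|---|
| Day 4 | 11 | 12 |
| Day 8 | 7 | 8 |
| Day 10 | 5 | 6 |

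A later onset widens the gap: onset on Day 4 gives Day 19, and onset on Day 8 gives Day 23. To prevent even one dose from a Day 1 onset, the required persistence could be at most *L* − 1 days: 3, 7 or 9 days for a last dose on Day 4, 8 or 10.

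**Two ways the bullet might still act**
1. The clock starts at Screening. With no Day 0, a sample on Day −14 would allow a stop from Day 2, and one on Day −7 from Day 9. That requires treating a child already above 5 × ULN. Exclusion 10 in Section 5.2 covers "clinically significant abnormal lab values reported at Screening Visit", and although it gives no numeric limit, it should keep such a child out.
2. The reschedule without a limit runs on to Day 15–16. The text allows this, but it is about a week beyond the planned window.

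**What an immediate stop on a persistent repeat could save.** Take the repeat at the full 48 hours, with that day's dose already given and results back the same day. Doses avoided = max(0, *L* − (*d* + 2)).
- *L* = 8: 5, 4, 3, 2, 1 for *d* = 1 to 5; 0 from Day 6.
- *L* = 4: 1 for *d* = 1; otherwise 0.
- *L* = 10: 7 for *d* = 1, falling by one per day to 0 from Day 8.
- Scheduled EOT sample (*d* = *L*): 0.

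For a 48-hour repeat these are upper bounds. The documents state no turnaround time, Section 8.4.1 sends samples to a central laboratory, and each day of delay removes a dose. A repeat taken sooner would shift the counts the other way by the days gained.

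**The case against.** The strongest reply is that the point has almost no practical reach. On the planned schedule the only on-treatment chemistry is drawn before the last dose at EOT, so the change saves nothing there, and the same is true of every laboratory stop in the table. A child tested off schedule will often have been tested because of symptoms, and the listed symptoms with ALT or AST above 3 × ULN already require an immediate stop. Section 9.1.1 lists circumstances in which drug must be stopped. Clinically significant laboratory abnormalities, at the physician's discretion, are among them, as is any situation that may put the child at risk. Section 10.2.1 says that a confirmed elevation leads to close observation with interruption considered, and to discontinuation if appropriate. Finally, stopping at a confirmed 5 to 8 × ULN is a stricter clinical threshold, supported here only by analogy with bilirubin.

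Most of this stands, and it sets the size of the point. What it does not answer is that the table's other laboratory stops can act on an early unscheduled test, whereas this bullet cannot. The routes in 9.1.1 and 10.2.1 depend on judgement; they do not make the mandatory bullet work. The threshold is a clinical choice for the sponsor, and nothing in the documents shows that a few doses fewer would change a child's risk.

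A reader might infer that children in this band have no protection, or that the statement in Section 4.5 is untrue. The documents support neither. The 48-hour repeat, monitoring to resolution, causality assessment and liver CRF all operate, including after the last dose. The ECG stops in 9.1.1 and the immediate-stop rows of Table 16-2 are specific stopping rules.

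**Conclusion.** The point holds for one bullet in one row. With dosing to Day 8, or about Day 10 if rescheduled by 1 to 2 days, the stop falls at least 5 to 6 days after the last dose even when the elevation is seen on Day 1. It cannot prevent a dose unless an open-ended reschedule carries dosing past Day 15–16. This assumes that the clock starts on or after Day 1, which exclusion 10 should ensure.

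The child affected has a confirmed elevation in this band, none of the features that already require an immediate stop, and an unscheduled test early enough before EOT. The dose counts should not be read as an expected saving: they rest on same-day results, which the documents do not support, and the documents give no frequency for such a child. Primary PK estimation and the sample-size reasoning are not in question. Severity is low: the change could be made.

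**What to change.** In the Table 16-2 row for ALT or AST above 5 and up to 8 × ULN, keep the 48-hour repeat and replace the second and third bullets (monitor, then stop after two weeks) with one bullet. It should carry the same instruction as the isolated bilirubin row, with persistence defined as a repeat still above 5 × ULN. Leave the third column as it is, so monitoring until resolution is retained. No hold on drug before the repeat is needed, so a child whose repeat falls below the threshold misses no dose and still meets the three-consecutive-day condition for PK sampling.

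The edit is small. The main cost is that a rare child may be stopped before the EOT PK profile. Section 5 replaces non-completers, so the target of 12 to 24 completers is unaffected, but the replacement is one more child dosed and bled (17 mL in total, Table 16-3). A stop driven by liver tests may also sit uneasily with the missing-completely-at-random assumption in Section 12.4.3.

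In a running trial the change would need an amendment with ethics approval (Section 14.1). SAP Section 1 records that this study ended early, so the correction now serves the protocol text itself and any further short-course study in which the table might be used.

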### 16.3 Appendix 3: Blood Volume Table

**Table 16-3 Blood volume**

Study phase	Time (h) 	Safety	PK		
			Dose Reference ID	Sample no.	mL
Screening (days -14 to -1)		5			
Treatment Day 1 (Baseline)					
End of Treatment	0 (pre-dose)	5	10  /11	101	1
	0.5		11	102	1
	1		11	103	1
	2		11	104	1
	3		11	105	1
	5		11	106	1
	8		11	107	1
Sub-total blood volume		10			7
TOTAL Blood volume (mL)					17

only one PK sample is collected at pre-dose, but the time difference to the doses on day prior to EOT and EOT day will be derived, requiring 2 dose reference IDs.  
Times are relative to the last dose on Day 4-8.

**Table 16-4 PK urine sample**

Study Visits	Time (h) 		PK urine Samples 		
	Start	End	Dose Reference ID	Sample No.	Volume (ml)
End of Treatment (Day 4-8)	0	8	11	201	2 x 1.5 mL

Times are relative to the last dose on Day 4- 8.  
Urine samples: Pre-dose, child should empty their bladder. This sample can be used for urine dipstick and then discarded. All urine from post-dose up to 8h will be pooled for analysis including urine dipstick.

## 16.4 Appendix 4: Pharmacokinetic/Vital signs/ECG/Lab assessment timed schedule (End of treatment)

**Table 16-5 PK/VS/ECG/Lab assessment schedule (EOT)**

Time point vs. 0 (dose time, hours)*	Vital Signs (Systolic/ diastolic BP /radial pulse)	ECG	PK	Hematology/ chemistry
Pre-dose	x	x	X*	x
0.5			X	
1			X	
2	x	x	X	
3			X	
5			X	
8			X	

Note: For Time points where multiple procedures occur, the following order is recommended: e.g. vital signs, PK, and lab. The PK blood draw should be as close as possible to the scheduled time.

\*In case a local anesthetic is used for placing the indwelling catheter, the time for it to take effect has to be accounted for prior to any assessment.

## 16.5 Appendix 5: Definition of pharmacokinetic parameters

**Table 16-6 Pharmacokinetic parameters**

Parameter	Definition
AUC 0-24h,ss	The AUC calculated to the end of a dosing interval (24 h) at steady-state (amount x time x volume  )
C max,ss	The maximum (peak) observed plasma concentration at steady state (mass x volume  )
T max,ss	The time to reach maximum (peak) plasma concentration at steady state (time)
C min,ss	The minimum observed plasma concentration at steady state (mass x volume  )
A e	The amount of drug excreted into urine (mass); can be used to derive a fraction of the dose excreted into urine (%)
CL/F	The total body clearance of drug from the plasma following extravascular administration (volume x time  )
CL r	The renal clearance of drug from the plasma (volume x time  )
(CL/F)/kg	The total body clearance of drug from the plasma following extravascular administration normalized to body weight ((volume x time  )/kg)

